1.0 Objectives

- 1.1 *Describe the purpose, specific aims, or objectives.*
- 1.2 *Response: The purpose of this study is to measure the reinforcing value of a preferred health snack food and an unhealthy snack food. We will also look at the reinforcing value of exercise and how these values may lead to long term weight gain in adolescents.*

- 1.3 *State the hypotheses to be tested.*

Response: *We hypothesize that sensitization to HED food will be associated with greater weight at the time of testing as well as greater weight gain over time, while sensitization to LED food will be associated with lower BMI percentile at the time of testing in adolescents.*

2.0 Background

- 2.1 *Describe the relevant prior experience and gaps in current knowledge.*

Response: *While a substantial body of research suggests that RRV is related to obesity, there is very little research on factors that contribute to the RRV of food, particularly how patterns of eating can increase or decrease the motivation to eat specific foods. Our previous work has demonstrated that a subset of obese individuals show increases in RRV of food after repeated consumption of large portions of HED snack foods, which we have conceptualized as sensitization. Our preliminary data suggest that sensitization of the RRV of HED food is a predictor of weight gain over time. However, more work needs to be done to address this relationship using a planned, prospective study design, using adolescent research subjects, and examining potential moderators of this relationship.*

- 2.2 *Describe any relevant preliminary data.*

Response:

We have strong preliminary data to suggest that increases in the RRV of food after repeated administration of LED and HED snacks meet the criteria for sensitization. Furthermore, sensitization to HED food is associated with greater weight at the time of testing as well as greater weight gain over time, while sensitization to LED food is associated with lower BMI percentile at the time of testing in adolescents. Finally, the relationship between sensitization to repeated food intake and BMI percentile is moderated by Delay Discounting, supporting previous work suggesting that reinforcement pathology is a risk factor for obesity ³². Our work and that of others from the past decade provides the foundation for this theoretical approach. The proposed studies will allow us to determine the

extent to which sensitization of the RRV of snack foods is predictive of weight gain and the development of obesity in adolescents. In addition, our preliminary data in adolescents suggest that sensitization to LED food may protect against weight gain.

2.3 Provide the scientific or scholarly background for, rationale for, and significance of the research based on the existing literature and how will it add to existing knowledge.

Response: This line of research will allow us to not only identify factors that increase risk for weight gain, but may also allow us to determine factors that protect against weight gain and obesity. If sensitization to LED food confirmed as a protective factor against weight gain in adolescents, future studies may focus on determining ways in which to sustain long-term increases the RRV of LED foods in order to promote LED food consumption and reduce weight gain. Finally, the proposed studies will also examine the independent and moderating effects of the RRV of physical activity to include a more comprehensive understanding of energy balance. If RRV of physical activity moderates the impact of sensitization of the RRV of HED food on weight change over time, developing strategies to increase the RRV of physical activity may provide an alternate pathway to prevent obesity among adolescents who do not find LED foods very reinforcing.

2.4 Include complete specific citations/references.

Response:

3.0 Inclusion and Exclusion Criteria

3.1 Describe the criteria that define who will be included or excluded in your final study sample.

Response: Two hundred twenty-six participants (113 boys, 113 girls) ages 12 – 16 will be studied.

Part 1:

INCLUSION:

- between 12-14yoa (male and female)
- zBMI: -1.5 to +2.0 (*determined by Height/weight measurement at Visit 1)
- neutral or higher liking of the study foods

EXCLUSION:

- Under/over age 12-16
- metabolic or endocrine disorder

- use of medications known to effect appetite (Ritalin, Adderall, Concerta, Wellbutrin, Prednisone, etc)
- Unwilling to complete the study visits
- allergy to study foods
- dislike of study foods (*determined via Preference for Study foods forms at Visit 1)
- parent report that child reads below 4th grade reading level
- parent report that child cannot complete light physical activity without assistance
- No English Speaking parent or legal guardian (therefore cannot provide consent in English nor answer questionnaires for this study)

* all other exclusion criteria are assessed from Survey monkey screening in advance of the first appointment vis parental report. At the first appointment the child is directly asses for height, weight, and The linking of study foods.

Part 2: Any subject completing V9 of part one who signed an addendum giving permission for future contact, will be invited to participate in Part 2 of the SNAK study. All interested former participants will be eligible to participate until age 18.

Part 3: Any subject completing V12 of part two who signed an addendum giving permission for future contact, will be invited to participate in Part 3 of the SNAK study.

At the age of 18 they may still participate, but will then be consented as an adult (rather than assented). If their parents are willing, they can accompany the participant to the appointment for collection of parent data (surveys, height/weight) or the forms can be sent to the parent for submission remotely.

3.2 Describe how individuals will be screened for eligibility.

Response: A survey monkey questionnaire “*SNAK Screening Survey 6.25.18.pdf*” will be used to screen all participants. This screening begins with a consent process prior to screening. The online screening (or phone screening when someone discloses that they do not have internet access) inquires about child date of birth, height/weight, liking of study foods, health conditions, allergies, and current use of medications. A participant is not eligible if they are allergic to a critical mass of the study foods, they are on medications effecting their eating.

At the first appointment the child is directly assessed for height, weight, and the linking of study foods. They must like at least one of the health and one of the junk foods 50% or more in order to participate. Additionally the BMI z score must fall into the range of -1.5 to 2.0 in order to stay in the study after Visit 1. For those that qualify at the end of Visit 1, they will not be reassessed for these criteria after Visit 1. Therefore the only exclusion criteria after visit 1 will be ability to schedule and attend study appointments.

3.3 *Indicate specifically whether you will include or exclude each of the following special populations: (You may not include members of these populations as subjects in your research unless you indicate this in your inclusion criteria.)*

- *Adults unable to consent*
- *Individuals who are not yet adults (infants, children, teenagers)*
- *Pregnant women*
- *Prisoners*

Response: Including individuals who are not yet adults.

3.4 *Indicate whether you will include non-English speaking individuals. Provide justification if you will exclude non-English speaking individuals.*

(In order to meet one of the primary ethical principles of equitable selection of subjects, non-English speaking individuals may not be routinely excluded from research. In cases where the research is of therapeutic intent or is designed to investigate areas that would necessarily require certain populations who may not speak English, the researcher is required to make efforts to recruit and include non-English speaking individuals. However, there are studies in which it would be reasonable to limit subjects to those who speak English: e.g., pilot studies, small unfunded studies with validated instruments not available in other languages, numerous questionnaires, and some non-therapeutic studies which offer no direct benefit.)

Response: This study will not include children that do not speak English, while we may be able to include families where English is the second language of the parent. This study is longitudinal and requires many questionnaires that have been validated in English, so it is a requirement that the participant speak English.

4.0 Study-Wide Number of Subjects (Multisite/Multicenter Only)

4.1 *If this is a multicenter study, indicate the total number of subjects to be accrued across all sites.*

Response: n/a

5.0 Study-Wide Recruitment Methods (Multisite/Multicenter Only)

If this is a multicenter study and subjects will be recruited by methods not under the control of the local site (e.g., call centers, national advertisements) describe those methods. Local recruitment methods are described later in the protocol.

5.1 *Describe when, where, and how potential subjects will be recruited.*

Response: Part 1: Upon approval, we will email a description of the screening survey along with a hyperlink to the survey to our contact database. We will also post flyers up on UB campus', in the community and distribute flyers to local schools, ever few months until all 226 participants have had their initial appointments. Facebook may be utilized for recruitment by simply posting our approved 4x6 refer a friend flyer on Facebook and asking people to like and share the flyer image.

5.2 *Describe the methods that will be used to identify potential subjects.*

Response: Part 1: Passive advertising via flyers and emails to our lab's consented contact database. We will also distribute flyers to schools and after school programs who have approved distribution of the study materials.

Part 2: Those that gave permission for future contact, should the SNAK study be extended, will be invited to participate in Part 2 of the SNAK study via email and phone script (attached).

Part 3: Those that gave permission for future contact, should the SNAK study be extended, will be invited to participate in Part 3 of the SNAK study. At this time, we will schedule their follow up appointment at the end of their previous appointment and only call families to notify them if the study is NOT extended (NIH grant extension not funded).

Those currently enrolled in the SNAK Part 1 will receive a flyer announcement about the future opportunity.

5.3 *Describe materials that will be used to recruit subjects. (Attach copies of these documents with the application. For advertisements, attach the final copy of printed advertisements. When advertisements are taped for broadcast, attach the final audio/video tape. You may submit the wording of the advertisement prior to taping to preclude re-taping because of inappropriate wording, provided the IRB reviews the final audio/video tape.)*

Response: Email recruitment and flyers to schools will be the main form of recruitment used for this study.

6.0 Multi-Site Research (Multisite/Multicenter Only)

6.1 *If this is a multi-site study where you are the lead investigator, describe the processes to ensure communication among sites, such as:*

- *All sites have the most current version of the protocol, consent document, and HIPAA authorization.*
- *All required approvals have been obtained at each site (including approval by the site's IRB of record).*
- *All modifications have been communicated to sites, and approved (including approval by the site's IRB of record) before the modification is implemented.*
- *All engaged participating sites will safeguard data as required by local information security policies.*
- *All local site investigators conduct the study appropriately.*
- *All non-compliance with the study protocol or applicable requirements will be reported in accordance with local policy.*

Response: n/a

6.2 *Describe the method for communicating to engaged participating sites:*

- *Problems.*
- *Interim results.*
- *The closure of a study*

Response: n/a

7.0 Study Timelines

7.1 *Describe the duration of an individual subject's participation in the study.*

Response: Part 1: The participant will participate in 9 visits over 2 years.

Part 2: Participants completing part 1 will be invited to take place in Part 2. This may include up to 3 visits; 1 every 9 months (up to a total of 3 appointments) prior to the participant turning 18 yo. Should a scheduled appointment occur after the participant's 18th birthday, they will be given a new consent process, upon arrival, for the legal adult participant.

7.2 *Describe the duration anticipated to enroll all study subjects.*

Response: We expect that it will take 3 years to enroll all participants in part 1 of the study.

7.3 *Describe the estimated date for the investigators to complete this study (complete primary analyses)*

Response: We expect that Part 1 of this study will be completed 5 years from the start date (approximately 2021).

Those that complete Part 1 in early 2021 and elect to participate in Part 2, may be participating until early 2023.

8.0 Study Endpoints

8.1 *Describe the primary and secondary study endpoints.*

Response: The primary endpoint is enrolling all 226 participants, and the secondary endpoint is completing all of their follow up visits for each participant.

8.2 *Describe any primary or secondary safety endpoints.*

Response: n/a

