Title: University at Buffalo Study of Nutrition and Activity in Kids (UB-SNAK)

Date updated: July 2, 2020

IRB approved: July 13, 2020

Hypotheses:

- 1) We hypothesized that sensitization to HED food is positively associated with zBMI gain over time
- 2) Sensitization to LED food is negatively associated with zBMI gain over time
- 3) Sensitization of HED and LED would interact with one another to impact zBMI change
- 4) The relationship between sensitization to HED food and zBMI gain is moderated by DD.

Sample Size Determination and Analytic Plan:

The sample size for this study was based on our prior studies in adults (Temple et al., 2014; Clark et al., 2010) that examined the relationship between sensitization, BMI, and weight change (effect size 0.19). We determined that, with an alpha of 0.05 and a power of 0.80, statistical significance could be achieved with a total of 180 participants.

In order to assess changes in zBMI over time and to account for missing values, we used multilevel modeling. To assess whether covariates are related to missingness, we examined baseline difference between those with complete versus incomplete data. There were no significant differences between these groups for child and parent BMI, race, sensitization, pubertal development, and food insecurity (all $p > 0.05$). We examined the scatterplots of zBMI data with each independent variable and observed that the data are linear.

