To test our primary hypotheses related to zBMI change over time, appointments (level 1) were nested within individuals (level 2) and models included month of visit, sex, DEBQ score, pubertal development score and baseline zBMI as fixed effects. Our dependent measure was zBMI at baseline and 6, 15, and 24 months. We used number of months between visits as our marker of time (i.e. 6, 15, and 24). To test hypotheses related to sensitization, we categorized people as “sensitizers” (> 1) or “satiators” (≤ 1) depending on their change in RRV of food from baseline to post. This threshold was chosen to account for participants who increased responding from baseline to post, even by a small amount, while allowing participants who did not change responding or who decreased responding to be considered together as satiators. To test hypothesis 1, we included HED sensitization in the model and examined interactions with time. To test hypothesis 2, we included LED sensitization in the model and examined interactions with time. To test hypothesis 3, we included both HED and LED sensitization in the model, we interacted each one individually with time, and we interacted them with each other and with time. Finally, to test hypothesis 4, we added DD as a fixed effect and interacted it with HED sensitization and visit to examine moderation.

- 1) Temple, J. L. Factors that influence the reinforcing value of foods and beverages. *Physiol. Behav.* **136**, 97-103, doi:10.1016/j.physbeh.2014.04.037 (2014).
- 2) Clark, E. N., Dewey, A. M. & Temple, J. L. Effects of daily snack food intake on food reinforcement depend on body mass index and energy density. *Am. J. Clin. Nutr.* **91**, 300-308, doi:10.3945/ajcn.2009.28632 (2010).

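### Protocol 8.1 makes an enrolment count the primary endpoint, and the SAP, which does fix zBMI as the outcome, neither ranks its four hypotheses nor says which one the sample size serves

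*Protocol*

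**What the plan says.** **Protocol 8.1** gives, as its whole answer on primary and secondary endpoints: "The primary endpoint is enrolling all 226 participants, and the secondary endpoint is completing all of their follow up visits for each participant."

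**Protocol 1.3** states hypotheses about weight. HED sensitization is expected to go with higher weight at testing and more weight gain later. LED sensitization is expected to go with lower BMI percentile at testing only.

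**Protocol 11.1** plans two-way ANOVAs with food reinforcement as the dependent variable and sex and BMI as predictors. **Protocol 11.2** gives power for a three-level dependent variable and two two-level independent variables.

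**The SAP** uses zBMI at baseline, 6, 15 and 24 months in a multilevel model. It lists four hypotheses:

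- H1: "sensitization to HED food is positively associated with zBMI gain over time"
- H2: "Sensitization to LED food is negatively associated with zBMI gain over time"
- H3: "Sensitization of HED and LED would interact with one another to impact zBMI change"
- H4: "The relationship between sensitization to HED food and zBMI gain is moderated by DD"

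The analysis text opens with "To test our primary hypotheses related to zBMI change over time", in the plural, and then describes a model for each. For H3 the two sensitization terms are each interacted with time and "we interacted them with each other and with time". The SAP gives no order, alpha split or multiplicity adjustment. Its one sample-size statement cites earlier adult studies of sensitization, BMI and weight change, an effect size of 0.19, alpha 0.05 and power 0.80, and concludes that "statistical significance could be achieved with a total of 180 participants".

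**The concern.** Accrual and retention are feasibility targets. Read literally, the study meets its primary endpoint whatever happens to zBMI.

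The SAP supplies the missing outcome but not the missing test. With four unranked hypotheses under one primary label, a significant result on any of them could be presented as the primary result, and a reader could not tell a planned choice from a later one. The stated alpha and power describe no named test. They give no assurance about H3 or H4, each of which adds a second factor to an effect that is already an interaction with time.

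**Working it through.** **1. The outcome in each place**

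| Place | Outcome |
|---|---|
| Protocol 8.1 | Enrolment (226); visit completion |
| Protocol 11.1 | Food reinforcement |
| SAP | zBMI at baseline, 6, 15 and 24 months |

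The outcome is inconsistent across the documents. Within the SAP it is single and clear.

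**2. Reproducing N = 180**

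Inputs from the SAP: effect size 0.19, alpha 0.05, power 0.80. Metric and sidedness are not stated. Reading 0.19 as a correlation, N = ((z_alpha + z_power) / atanh(0.19))² + 3, with atanh(0.19) = 0.1923:

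- two-sided: ((1.960 + 0.842) / 0.1923)² + 3 = 215.2, so 216
- one-sided: ((1.645 + 0.842) / 0.1923)² + 3 = 170.1, so 171

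Other readings:

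- f = 0.19: 218 to 220 two-sided, 172 one-sided
- d = 0.19: 870 two-sided
- f² = 0.19: 44 to 88 for 1 to 8 tested degrees of freedom
- repeated-measures between-group test, f = 0.19, three measures: 176 if the correlation is 0.7, but the documents give no correlation

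So 180 is not recovered from the stated inputs alone. For the two-sided correlation, power is Φ(√(N − 3) × 0.1923 − 1.960):

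- N = 180: Φ(2.559 − 1.960) = 0.725
- N = 226: Φ(2.872 − 1.960) = 0.819

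The power statement in Protocol 11.2 concerns a different design and cannot fill the gap.

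**3. Chance of at least one false positive**

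Assumption: four tests, each two-sided at 0.05.

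- Independent: 1 − 0.95⁴ = 0.185
- Upper bound under any dependence: 4 × 0.05 = 0.20
- Equally correlated test statistics (simulated; correlations assumed): 0.174 at 0.3, 0.156 at 0.5, 0.130 at 0.7, 0.094 at 0.9

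One named primary test holds it at 0.05.

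**4. Power for H3**

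Assumptions: H1 truly has power 0.80, so its noncentrality is 1.960 + 0.842 = 2.80; the HED × LED effect on change is as large as the H1 effect; HED and LED status are unrelated; a share q are LED sensitizers. The standard error grows by 1/√(q(1 − q)):

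- q = 0.5: factor 2.00, noncentrality 1.40, power Φ(1.40 − 1.96) = 0.29
- q = 0.3: factor 2.18, noncentrality 1.28, power Φ(1.28 − 1.96) = 0.25

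This holds for a binary second factor only, so it says nothing about H4.

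**The case against.** The strongest reply is that the SAP is clear enough. It names one dependent measure, its measurement times, and a model for each hypothesis. That stands for the outcome: a reader might infer from Protocol 8.1 that no analysable outcome is fixed anywhere, and the SAP shows otherwise.

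Four further readings are tempting, and the documents do not support them.

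- *That the SAP declares four primary tests at 0.05 each.* It speaks of primary hypotheses, and alpha appears once, in the sample-size sentence. Four tests at 0.05 is the natural inference, since every listed hypothesis concerns zBMI change and none is called secondary, but it is an inference.
- *That 18.5% is the error rate.* It assumes independence, although the tests share participants and outcome, and H1, H3 and H4 share HED sensitization. H1 and H2 are also directional. Counting only predicted-direction results for those two gives 1 − 0.975² × 0.95² = 14.2% under independence.
- *That only H3 and H4 are interactions with time.* H1 and H2 are as well. H3 and H4 differ in adding another factor.
- *That H4 shares the low power shown for H3.* Its moderator is delay discounting, for which the SAP states no dichotomy. For a standardised continuous moderator unrelated to HED status (assumption), an equal effect per standard deviation would lose no power by the same formula.

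It is also fair to say that choosing H1 as primary is a judgement. The absence of ranking, of a multiplicity rule and of a link to the sample size survives all of this.

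**Conclusion.** The point holds in a limited form. Protocol 8.1 names no endpoint that can answer the study question, and 11.1 conflicts with the SAP on the outcome. Within the SAP the outcome is fixed, but the primary test, its error rate and its power are not.

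If all four hypotheses are tested at 0.05, the familywise error is between about 9% and 20%, depending on a correlation that the documents do not give. Every value calculated exceeds 5%. The sample-size basis is closest to H1 and H2 and does not cover the added factor in H3 or the moderation in H4. Power of 0.25 to 0.29 for H3 is illustrative and rests on the assumptions listed with it.

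A reader might infer that the 0.80 power belongs to H1, or that 180 is wrong. Neither follows. The SAP ties 0.19 to no numbered hypothesis, and failure to recover 180 shows only that the metric, the sidedness or a further input is missing.

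**What to change.** - **Protocol 8.1:** make zBMI at baseline, 6, 15 and 24 months the primary endpoint. Move accrual and retention to feasibility targets.
- **Protocol 11.1 and 11.2:** align both with the SAP's multilevel model. Otherwise a zBMI endpoint would sit beside a food-reinforcement analysis.
- **SAP, primary test:** name HED sensitization × time (H1) as the single primary test. It is the only hypothesis on weight gain over time that appears in both Protocol 1.3 and the SAP. Label H2 to H4 secondary or exploratory. If the sponsor keeps all four as primary, apply a Holm adjustment.
- **SAP, sample size:** state the metric and sidedness of the 0.19 and the test it serves, and restate power for that test. For example, a two-sided correlation gives about 0.73 at N = 180, not 0.80. Say that no power is claimed for H3 and H4.

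No visit, procedure or participant number changes. The costs are two. H2 to H4 can no longer be presented as primary results; under Holm they could be, but the smallest p-value must then pass 0.05/4 = 0.0125, a threshold at which power for a single test would be about 0.52 at N = 180 on the same correlation reading. Also, the SAP already reports missingness comparisons and scatterplots of zBMI against each independent variable, so the designation must be dated and disclosed as made after data inspection. That weakens its value as a prior commitment but does not remove the need for it.
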